3.4 Efficacy Analyses

3.4.1 Primary Efficacy Endpoint Analyses

3.4.1.1 Primary Efficacy Endpoint

The primary endpoint is the time (days) from Day 1 to onset of an AC-determined NMO/NMOSD attack on or before the end of RCP (Day 197/discontinuation visit). The definition of an NMO/NMOSD attack is the presence of a new symptom(s) or worsening of an existing symptom(s) related to NMO/NMOSD that meets at least ONE of the protocol-defined criteria for an NMO/NMOSD attack provided in Table 3.4.1.4-1. This table is displayed only to pre-specify the severity grading attached to each criterion which is not presented in the protocol to eliminate any possible bias by the site when assessing for an attack. Onset day is defined as when the subject visits the site for possible attack assessment (ie, the initiation of attack assessment visit).

Per protocol requirement, sites are required to schedule an Assessment Visit with the subject within 72 hours of symptoms being reported or identified and all assessments are to be completed within 5 days of this visit. However, not all AC-determined attacks may fall within these time windows; hence a broader window will be used for primary analysis. **Only AC-determined attacks with an assessment visit scheduled within 120 hours (5 days) of reporting symptoms AND all necessary assessments done within 10 days of an Assessment Visit will be included in the primary analysis.** Other AC-determined attacks not included in primary analysis will be included in other supportive analyses.

3.4.1.2 Handling of Dropouts and Missing Data

No imputation will be performed for missing data for primary analysis.

3.4.1.3 Primary Efficacy Analysis

The following are the null and alternative hypotheses associated with the primary endpoint:

$$H_{01}: HR^+ = 1 \text{ vs } H_{11}: HR^+ \neq 1,$$

$$H_{02}: HR^{ALL} = 1 \text{ vs } H_{12}: HR^{ALL} \neq 1,$$

where HR^+ indicates the hazard ratio of AC-determined NMO/NMOSD attack for MEDI-551 relative to placebo in AQP4-IgG seropositive subjects. HR^{ALL} denotes the same quantity for the ITT population. The treatment effect in the seropositive cohort will be defined as the relative reduction in HR^+ ; ie, $100 \times (1 - HR^+)$. A value of $HR^+ < 1$ or a positive value of relative reduction will indicate the efficacy of MEDI-551 compared to placebo in the seropositive cohort. Similar interpretations will hold for HR^{ALL} . For the current study, the target treatment effect of 60% implies a hazard ratio (HR) of 0.4.

For the AQP4-IgG seropositive cohort, the treatment effect will be assessed using the Cox proportional hazards model with treatment indicator (MEDI-551 or placebo) as an explanatory factor; whereas for the ITT population, the model will also include serostatus as an additional explanatory factor. The HR of MEDI-551 versus placebo will be estimated together with its associated 95% CI. The SAS PROC PHREG will be used for fitting this model. Subjects who complete the Day 197 visit of the RCP or discontinue the study before Day 197 for reasons other than an AC-determined NMO/NMOSD attack will be censored in this model at the time of the Day 197/discontinuation visit.

An indicator variable for Japan versus non-Japan region will not be included in the Cox regression model due to the low number of anticipated Japanese subjects. An evaluation of consistency of treatment effect in Japanese subjects with that observed in the global study will be determined.

The data cutoff date for the primary analysis will be when the last subject completes the discontinuation visit following the 67th AC-determined attack, or after all subjects complete the RCP if 67 AC-determined attacks do not occur, or when the last subject completes the discontinuation visit following discontinuation of enrollment upon recommendation of the DMC based on evidence of efficacy and safety. Subjects who are in the RCP when a total of 67 AC-determined NMOSD attacks have occurred, or when enrollment is discontinued upon

recommendation of the DMC based on evidence of efficacy and safety, will discontinue the RCP as soon as possible, preferably within 14 days.

The procedure for the Type I error control for the primary analysis of AQP4-IgG seropositive subjects, the primary analysis of ITT population and the key secondary endpoints is described in Appendix 3.

3.4.1.4 Additional and Sensitivity Analyses of the Primary Efficacy Endpoint

An estimate of the cumulative event rates at the end of the RCP and median time to event will be calculated using the KM method. Graphical displays of KM estimates and cumulative incidence estimates will be presented by treatment group.

Following sensitivity analyses of the primary endpoint will be performed:

1. Analysis using the Cox regression model with following baseline characteristics and treatment as explanatory variables:
 - Number of prior NMO/NMOSD relapses
 - Baseline EDSS score
2. Analysis similar to primary analysis (attacks from all strata) based on unanimous adjudicated attacks (all three adjudicators agree) as events, remaining subjects will be considered as censored.
3. Analysis similar to primary analysis (attacks from all strata) including subjects who prematurely discontinue the RCP without experiencing an AC-determined attack as treatment failures (events), remaining subjects will be considered as censored.
4. Analysis similar to primary analysis (attacks from all strata) including SFP data for subjects who prematurely discontinue the RCP without experiencing an AC-determined attack. Attack data from the SFP up to 204 days after the subject's initial randomisation will be used in the analysis for subjects who prematurely discontinue the RCP. If the subject did not have an attack in the SFP before or on Day 204 then they will be censored at Day 204.
5. Analysis similar to primary analysis (attacks from all strata) based on only clinical criteria (ie excluding attacks that require MRI dependent criteria), remaining subjects will be considered as censored.
6. The impact of the loss of attacks outside of the attack assessment windows in the primary analysis will be evaluated. The AC-determined attacks falling into different attack assessment windows will be analysed similarly to primary analysis.
 - a. Attacks regardless of attack assessment window;

- b. Attacks with an assessment visit scheduled within 72 hours (3 days) of reporting symptoms and all assessments done within 5 days of an Assessment Visit;
 - c. Attacks with an assessment visit scheduled within 72 hours (3 days) of reporting symptoms regardless whether all assessments are done within 5 days of an Assessment Visit;
7. The impact of attacks with onset before the full pharmacodynamic effect of MEDI-551 has been reached will be evaluated. Subjects with AC-determined attacks with onset on or before Day 15 will be censored at the time of the attack.
8. Analysis similar to primary analysis including AC-determined attacks up to and including January 27, 2017, remaining subjects will be censored on January 27, 2017 (the Sponsor received a recommendation from IDMC to stop enrollment and conclude the RCP of the study as early as January 27, 2017).

Consistency of treatment effect observed in Japanese subjects with global treatment effect may be assessed by the ratio of hazard ratios (HR) as $HR(\text{Japan})/HR(\text{Global})$, where respective HR estimate is obtained from Cox proportional hazards model based on respective population.

Table 3.4.1.4-1 Protocol-defined Criteria for an NMO/NMOSD Attack with criteria based severity

Attack Type	Protocol-defined Attack Criteria (with severity grading)
ON	
 1. Greater than 15-character drop in high-contrast Landolt C Broken Rings Chart from last visit as measured in a previously affected eye and no other ophthalmological explanation (Severe) 2. At least 2-step drop in CF to NLP from last visit as measured in a previously affected eye and no other ophthalmological explanation (Severe) 3. At least 7 or more character drop in low-contrast Landolt C Broken Rings Chart from last visit as measured in either eye alone (monocular) AND a new RAPD in affected eye (Moderate) 4. At least 7 or more character drop in low-contrast Landolt C Broken Rings Chart from last visit as measured in either eye alone (monocular) AND loss of a previously documented RAPD in fellow eye (Moderate) 5. At least 5 or more character drop in high-contrast Landolt C Broken Rings Chart from last visit as measured in either eye alone (monocular) AND a new RAPD in affected eye (Mild) 6. At least 5 or more character drop in high-contrast Landolt C Broken Rings Chart from last visit as measured in either eye alone (monocular) AND loss of a previously documented RAPD in fellow eye (Mild) 7. At least 1-step drop in CF to NLP from last visit as measured in a previously affected eye AND a new RAPD in affected eye (Moderate) 8. At least 1-step drop in CF to NLP from last visit as measured in a previously affected eye AND loss of a previously documented RAPD in affected eye (Moderate) 9. At least 7 or more character drop in low-contrast Landolt C Broken Rings Chart from last visit as measured in either eye alone (monocular) AND a new Gd-enhancing or new/enlarging T2 MRI lesion in the corresponding optic nerve (Moderate) 10. At least 5 or more character drop in high-contrast Landolt C Broken Rings Chart from last visit as measured in either eye alone (monocular) AND a new Gd-enhancing or new/enlarging T2 MRI lesion in the corresponding optic nerve (Mild) 11. At least 1-step drop in CF to NLP from last visit as measured in a previously affected eye AND a new Gd-enhancing or new/enlarging T2 MRI lesion in the corresponding optic nerve (Moderate)

Table 3.4.1.4-1 Protocol-defined Criteria for an NMO/NMOSD Attack with criteria based severity

Attack Type	Protocol-defined Attack Criteria (with severity grading)
Myelitis	12. At least 2-point worsening in 1 or more of the relevant (pyramidal, bladder/bowel, sensory) FSS compared to last visit (Severe) 13. At least 1-point worsening in EDSS score compared to last visit if previous EDSS score is 5.5 or more (Severe) 14. At least 1-point worsening in 2 or more of the relevant (pyramidal, bladder/bowel, sensory) FSS compared to last visit AND a new Gd-enhancing or new/enlarging T2 MRI lesion in the spinal cord (Moderate) 15. At least 0.5-point worsening in EDSS score compared to last visit if previous EDSS score is 5.5 or more AND a new Gd-enhancing or new/enlarging T2 MRI lesion in the spinal cord – (Severe)
Brainstem	16. Isolated (not present at last visit) intractable nausea, vomiting, and/or hiccups lasting for greater than 48 hours AND a new Gd-enhancing or new/enlarging T2 MRI lesion in the brainstem (Severe) 17. At least 2-point worsening in 1 or more of the relevant (brainstem, cerebellar) FSS compared to last visit AND a new Gd-enhancing or new/enlarging T2 MRI lesion in the brainstem (Severe)
Brain	18. At least 2-point worsening in 1 or more of the relevant (cerebral, sensory, pyramidal) FSS (with a score of 3 or more at the current visit) compared to last visit AND a new Gd-enhancing or new/enlarging T2 MRI lesion in the brain consistent with the clinical presentation (Severe)

CF = counting fingers; EDSS = Expanded Disability Severity Score; FSS = Functional System Scores; Gd = gado linium; HM = hand motion; LP = light perception; MRI = magnetic resonance imaging; NLP = no light perception; NMO/NMOSD = neuromyelitis optica/neuromyelitis optica spectrum disorders; ON= optic neuritis; RAPD = relative afferent pupillary defect.

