4.1.5 Withdrawal from the Study

Subjects are at any time free to withdraw from the study (investigational product and assessments), without prejudice to further treatment (withdrawal of consent). Such subjects will always be asked about the reason(s) and the presence of any AEs.

Subjects in the RCP who express a wish to prematurely discontinue from the study will be followed for protocol-specified assessments until Day 197, unless consent is withdrawn specifically for further study participation. In this case the subject will complete the SFP unless the subject is lost to follow up, or the subject is enrolled in another clinical study. Subjects who discontinue from the OLP will enter the SFP, if possible.

In the Czech Republic only, subjects may discontinue from the investigational product and, following an Early Discontinuation Visit (EDV), subjects will enter the SFP if they agree to this safety follow up; unless the subject is lost to follow up, or the subject is enrolled in another clinical study.

Diaries and all study medications should be returned by the subject. If a subject withdraws consent from further participation in the study, then no further study visits or data collection should take place.

A subject's decision to withdraw from treatment must be documented in the source documents.

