4.2.2 Treatment Period

4.2.2.1 Randomized-controlled Treatment Period

Randomization will occur on Day 1 (within 28 days of the start of screening, unless screening is extended as noted above). Table 6 shows all procedures to be conducted during the Randomized-controlled treatment period. Patient-reported outcomes should be done first followed by all other assessments/procedures in an order determined by the site. All procedures must be completed prior to administration of investigational product. If necessary, the randomization visit may be split over 2 days, in this case randomization and investigational product administration must occur on the second day. If a subject discontinues from the study early during the RCP, all procedures should be conducted as presented in Table 6 for the Day 197/ EDV. If a subject withdraws from the study, every attempt should be made to have the subject come to the site to conduct EDV assessments.

If a subject withdraws during a scheduled study visit, that visit will change to an EDV and procedures should be conducted according to those presented for Day 197/EDV. Following an EDV, all subjects should continue into the SFP.

At the time 67 AC-determined attacks have occurred or when enrollment is discontinued upon recommendation of the independent DMC based on evidence of efficacy and safety, the sponsor will notify all sites and the sites will notify all subjects who are in the RCP that these subjects must discontinue the RCP as soon as possible, preferably within 14 days, and should be given the option to enroll into the OLP. Procedures should be conducted as presented in Table 6 for the Day 197/ EDV; however, subjects who have had an MRI in the last 3 months need NOT repeat the MRI. Subjects who decide to enroll into the OLP will follow the procedures of the OLP presented in Table 7.

Table 6 Schedule of Randomized-controlled Treatment Period Study Procedures

Study Period	Randomized-controlled Period												
	0	1	2	4	8	12	16	22	28/EDV				
Week													
Day	1 ^h	8	15	29	57	85	113	155	197				
Visit Window		± 1d	± 3d	± 3d	± 3d	± 3d	± 3d	± 3d	± 7d				
Procedure / Visit Number	2	3	4	5	6	7	8	9	10				
Verify eligibility criteria	X												
SF-36v2 Health Survey ^a	X					X			X				
Pain NRS	X			X	X	X	X	X	X				
Modified Rankin Scale	X			X	X	X	X	X	X				
Medical and disease history (including smoking and alcohol history)	X												
C-SSRS (“Since Last Visit” version) ^g	X	X	X	X	X	X	X	X	X				

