4.2.6 Safety Follow-up Period

Table 10 shows all procedures to be conducted during the SFP.

The SFP will start when a subject prematurely discontinues from the RCP or the OLP. The length of the SFP will be determined by the time elapsed from the time of the last dose of the investigational product to the time of the premature discontinuation, to complete a total of 52 weeks. Subjects who prematurely discontinue during the RCP will continue with the study assessments until Day 197, unless the consent was specifically withdrawn for further study assessments.

Table 10 Schedule of Procedures for Safety Follow-up Period

Study Period	Follow-up Period
Visit Number	Every 3 months for a total of 1 year after last dose of investigational product (± 14d)
Procedure/Study	
Vital signs	X
C-SSRS (“Since Last Visit” version)	X
Whole blood for flow cytometry (B-cell count and cell subsets)	X
Total Ig, IgM, IgG, IgA, and IgE	X
MEDI-551 ADA	X
Assessment of AEs/SAEs	X

ADA = anti-drug antibody; AE = adverse event; C-SSRS = Columbia Suicide Severity Rating Scale; d = day(s); Ig A/E/G/M = immunoglobulin A/E/G/M; SAE = serious adverse event

[figure not shown]

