Appendix 1 Sample Size Calculation

The proposed study is being planned to detect a target relative reduction of 60% in risk for time (days) from Day 1 to onset of an AC-determined NMO/NMOSD attack on or before Day 197 with 90% power and $\alpha = 0.05$ (two-sided), assuming an unequal randomization ratio of 3:1 to MEDI-551 versus placebo. Using the following formula, a total of 67 AC-determined NMO/NMOSD attacks will be required:

$$E = \left[\frac{z_{1-\alpha/2} + z_{1-\beta}}{\ln(HR)} \right]^2 \times \frac{(r+1)^2}{r},$$

where $z_{1-\alpha/2}$ and $z_{1-\beta}$ are $100(1 - \alpha/2)^{\text{th}}$ and $100(1 - \beta)^{\text{th}}$ percentile of a standard normal distribution, $r = 3$ is the randomization ratio and $HR = \text{hazard ratio} = 0.4$.

Following the completion of the first 78 subjects in this study the sample size was reviewed. The attack rate of the first 78 subjects to complete the RCP was used to simulate the remaining subjects to estimate the probability of reaching the required 67 AC-determined attacks. The simulation showed that with a sample size of 252 subjects there is a 90% probability of reaching the required 67 AC-determined attacks.

The remaining text in this appendix describes the process of defining the original sample size of 212 subjects.

Assuming hazard rates of 1.5/year and 1.0/year for an NMO/NMOSD attack in the placebo arm for seropositive and seronegative groups, respectively, and using the following formula:

$$N = \frac{E}{\Pr(\text{Fail})},$$

a total of 212 (with an upward adjustment) subjects are expected to be enrolled in this study where

$$\Pr(\text{Fail}) = s_1 P_1 + s_2 P_2$$

is the weighted average of the failure probabilities P_1 and P_2 in seropositive and seronegative cohorts, respectively, with associated stratum specific weights $s_1 = 0.8$ and $s_2 = 0.2$. Recall that subjects will be enrolled to seropositive and seronegative cohorts in 80:20 ratio.

Furthermore, the probability of an attack within i^{th} cohort ($i = 1, 2$) is given by

$$P_i = (1 - w)p_{i0} + wp_{i1}$$

the weighted average of the failure probabilities p_{i0} and p_{i1} for placebo and MEDI-551 groups, respectively; $p_{i0} = 1 - e^{-\lambda_{i0}F}$, $p_{i1} = 1 - e^{-\lambda_{i1}F}$; $F = 197/365 = 0.54$ to indicate the 197 days (28 weeks) duration of the controlled portion of the study; note that based on the

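### Sensitivity analysis 4 censors early discontinuers at Day 204 whether or not their attack status was known that long, so it can credit unobserved attack-free time

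*SAP*

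**What the plan says.** **The rule.** SAP 3.4.1.4, item 4, takes subjects who leave the RCP early without an adjudicated attack, adds attack data from the SFP up to 204 days after randomization, and then states: "If the subject did not have an attack in the SFP before or on Day 204 then they will be censored at Day 204". Day 204 is the upper end of the Day 197 visit window of ±7 days (Protocol Table 6). The primary analysis censors the same subjects at their discontinuation visit (SAP 3.4.1.3).

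**What the SFP collects.** Protocol 4.2.6 states: "Table 10 shows all procedures to be conducted during the SFP". Table 10 lists, every 3 months, vital signs, C-SSRS, flow cytometry, immunoglobulins, anti-drug antibodies and AE/SAE review. The symptom-assessment row of Tables 6 and 7 is absent, as are EDSS, ophthalmology and MRI. Protocol 4.3.1.1 describes adjudication for RCP and open-label attacks only, and its two-weekly calls end with the RCP.

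**Passive capture.** Protocol 5.1 exempts attacks from AE recording only in the RCP and open-label period. Section 5.2 makes SFP attacks that meet SAE criteria reportable, and 5.4.1 collects AEs through the SFP.

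**Who is followed.** Protocol 4.1.5 says that subjects who wish to leave the RCP early "will be followed for protocol-specified assessments until Day 197" unless they withdraw consent for further participation; 4.2.6 repeats this. Section 4.2.2.1 says: "Following an EDV, all subjects should continue into the SFP", and 3.1.1.3 likewise sends those leaving the RCP to the SFP. Section 4.1.5 ends by stopping all visits and data collection once consent for participation is withdrawn.

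**The concern.** A censoring time should be the last time at which the subject was known to be event-free. Item 4 replaces it with a fixed calendar day. For a subject with no further contact after Day 60, say, the model receives 144 days (204 − 60) of attack-free risk time that nobody observed. Where ascertainment is passive, the absence of a recorded attack is weak evidence that none occurred.

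The added time dilutes the attack rate of the arm with more, or earlier, unfollowed dropout. Item 4 is there to show whether dropout distorts the primary result. If more MEDI-551 subjects leave, and those who leave are doing badly, it can move the hazard ratio away from the value that full follow-up would have given.

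**Working it through.** **1. Design inputs.** SAP Appendix 1 plans the trial "with 90% power and $\alpha = 0.05$ (two-sided), assuming an unequal randomization ratio of 3:1 to MEDI-551 versus placebo"; SAP 3.4.1.3 states "the target treatment effect of 60% implies a hazard ratio (HR) of 0.4"; Appendix 1 concludes "a total of 67 AC-determined NMO/NMOSD attacks will be required". Check:

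E = [(1.960 + 1.282) / ln 0.4]² × (3 + 1)²/3 = 66.75, rounded up to 67. The plan's figure is reproduced.

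**2. Attack rates.** Appendix 1 reads: "Assuming hazard rates of 1.5/year and 1.0/year for an NMO/NMOSD attack in the placebo arm for seropositive and seronegative groups, respectively". The 1.5/year rate is used below, and also 1.2/year as an assumption. The latter fits the blinded review: Protocol Appendix 9 gives 227 subjects for a 50% chance of 67 attacks, so 67/227 = 0.295. At 1.2/year with HR 0.4 and 0.54 years, the expected proportion is 0.25(1 − e^(−0.648)) + 0.75(1 − e^(−0.259)) = 0.119 + 0.171 = 0.290.

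**3. Assumptions that the documents do not supply.** Dropout by arm is assumed. Unless stated, no SFP attack is recorded and no discontinuer continues RCP assessments, so the percentages below are discontinuers with no further ascertainment.

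**4. Hand check.** Rate = attacks / person-time. With no capture, the rule adds time and no attacks. Take 5% placebo and 15% MEDI-551 dropout, uniform over Days 1–197, at rates λ of 1.5 and 0.6 per year.

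- Mean days at risk for stayers, (1 − e^(−0.54λ))/λ: placebo 135.0, MEDI-551 168.3. For leavers up to leaving: 76.9 and 89.1.
- Primary person-time per subject: placebo 0.95 × 135.0 + 0.05 × 76.9 = 132.1; MEDI-551 0.85 × 168.3 + 0.15 × 89.1 = 156.4.
- Unobserved time per leaver to Day 197, the mean over leaving day c of e^(−λc)(197 − c): 75.9 and 88.1 days. Added per subject: 0.05 × 75.9 = 3.8 and 0.15 × 88.1 = 13.2.
- Rates shrink by 132.1/135.9 = 0.972 and 156.4/169.6 = 0.922.
- HR = 0.40 × 0.922/0.972 = 0.379.

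**5. Cox simulation.** The 1.2/year rows use 252 subjects and 1,500 runs, with dropout uniform over Days 15–197. The 1.5/year rows use one cohort of 1,000,000, with dropout uniform over Days 1–197. Allocation is 3:1 throughout.

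| Dropout, placebo / MEDI-551 | Placebo rate per year | Primary HR | Item 4 HR | Full follow-up HR |
|---|---|---|---|---|
| 5% / 15% | 1.2 | 0.401 | 0.384 | 0.402 |
| 5% / 15% | 1.5 | 0.400 | 0.382 | 0.400 |
| 15% / 5% | 1.2 | 0.403 | 0.426 | 0.402 |
| 5% / 5% | 1.5 | 0.400 | 0.402 | 0.400 |
| 10% / 10% | 1.5 | 0.399 | 0.403 | 0.399 |
| 5% / 15%, half of SFP attacks captured | 1.5 | 0.399 | 0.390 | 0.399 |
| 5% / 15%, all captured | 1.5 | 0.401 | 0.401 | 0.401 |
| 5% / 15%, hazard doubled after dropout | 1.2 | 0.405 | 0.388 | 0.420 |
| 5% / 15%, true HR 1.0 | 1.5 | 1.004 | 0.948 | 1.004 |

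**6. Scale against noise.** With 67 events at 3:1, SE(log HR) ≈ √(16/3/67) = 0.282, so a 95% interval around 0.40 runs from about 0.23 to 0.70. The move from 0.401 to 0.384 is ln(0.401/0.384) = 0.043, or 0.15 SE.

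**The case against.** Three stronger readings are tempting, and the documents support none of them.

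- **That SFP attacks go unrecorded.** A reader might infer this from Table 10. Protocol 5.1, 5.2 and 5.4.1 provide passive, unadjudicated capture through AE/SAE reporting. Half capture roughly halves the shift, and full capture removes it.
- **That every early discontinuer is unobserved.** Sections 4.1.5 and 4.2.6 keep discontinuers who have not withdrawn consent on assessments to Day 197. The gap falls on those who decline, are lost, or go straight to the SFP. Section 4.1.5 itself routes some who withdraw consent into the SFP, so it conflicts with 4.2.2.1 less sharply than the two sentences suggest when read alone.
- **That the rule always flatters MEDI-551, or puts the main result in doubt.** Equal dropout barely moves the hazard ratio, and higher placebo dropout moves it toward 1. Item 4 is one of eight supportive analyses and carries no alpha. Item 3 counts early discontinuers as events and moves against the drug in the scenario that causes worry, so it is a partial counterweight.

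It can also be said that the effect is small, and that censoring at last ascertainment may simply return the primary result. Both are true. Neither justifies keeping risk time that was not observed. An analysis that falls back to the primary result for lack of data is more informative than one that appears to confirm it.

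**Conclusion.** The point stands, limited to one sensitivity analysis. As written, item 4 credits attack-free time to Day 204 without requiring that attack status was known, in a period with no scheduled or adjudicated attack assessment. The direction of the bias depends on the dropout imbalance. With a true HR of 0.40 and no capture, the result is about 0.38 (5% placebo, 15% MEDI-551), about 0.43 (15%, 5%), or about 0.40 (equal). The case that matters is higher MEDI-551 dropout among failing subjects: about 0.39 against 0.42 with full follow-up. That gap assumes that no SFP attacks are recorded, and it closes at full capture.

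These sizes rest on assumed dropout rates, constant hazards and discontinuers with no further assessment. They are small beside the sampling error and leave the primary test untouched. What is at risk is item 4's value as a check on dropout.

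**What to change.** 1. **SAP 3.4.1.4, item 4.** Censor at the earlier of Day 204 and the last date on which attack status was ascertained: an RCP-type assessment, or a documented contact or AE/SAE review that covered attacks. Use the same source for events and for censoring.
2. **SAP, same item.** State which SFP AE/SAE records count as attacks and whether they are adjudicated.
3. **Reporting.** Tabulate by arm how many discontinuers lack attack follow-up to Day 197.
4. **Protocol.** Reconcile 4.1.5 and 4.2.6 with 3.1.1.3 and 4.2.2.1 on whether a discontinuer who has not withdrawn consent stays on RCP assessments to Day 197 or moves to the SFP.

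The cost is a few sentences, one table and no new data collection. With non-informative dropout, the revised rule returns the primary value (0.40 under the design effect, 1.00 under the null). The downside is that, where little SFP ascertainment exists, item 4 will be close to the primary analysis and will not correct for informative dropout; the report should say so.
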